5.3 LIFESTYLE CONSIDERATIONS

Not applicable.

5.4 SCREEN FAILURES

Screen failures are defined as participants who consent to participate in the clinical study but are not subsequently randomly assigned to study intervention/entered in the study. A minimal set of screen failure information is required to ensure transparent reporting of screen failure participants to meet the Consolidated Standards of Reporting Trials (CONSORT) publishing requirements and to respond to queries from regulatory authorities. Minimal information includes demography, screen failure reasons, eligibility criteria, and any SAE.

In the case of technical malfunction of equipment, the patient may be rescreened. Patients who fail the exclusion criteria may be rescreened once during the open screening period of the study. Rescreened participants will be assigned a new participant number versus the one received for the initial screening.

There is no requirement for a waiting period between the screen-failure date and the rescreening date. The interactive response technology (IRT) report will flag rescreened patients. Patients that are rescreened must sign a new consent form and all Visit 1 procedures must be repeated.

If certain dynamic laboratory tests do not meet the eligibility criteria at screening, these laboratory assessments may be repeated, at the discretion of the Investigator, if it is judged to be likely to return to acceptable range for study inclusion within the screening visit window prior to Day 1. There is no need to screen fail such participants if the test finally meets the eligibility criteria.

6 STUDY INTERVENTION

Study intervention is defined as any investigational intervention(s), marketed product(s), placebo, or medical device(s) intended to be administered to a study participant according to the study protocol.

6.1 STUDY INTERVENTION(S) ADMINISTERED

Table 2 - Overview of study interventions administered

ARM name	Dupilumab	Placebo
Intervention name	Dupilumab 300 mg	Placebo matching dupilumab 300 mg
Type	Biological/Vaccine	Other
Dose formulation	A 150 mg/mL dupilumab solution in a pre-filled syringe to deliver 300 mg in 2 mL	Identical formulation to the active 300 mg formulation without dupilumab, in a pre-filled syringe to deliver placebo in 2 mL
Unit dose strength(s)	300 mg	0 mg (placebo)
Dosage level(s)	300 mg every 14 ±3 days after an initial loading dose of 600 mg	0 mg every 14 ±3 days with a loading dose of 0 mg
Route of administration	Subcutaneous ^a	Subcutaneous ^a
IMP and NIMP	IMP	IMP
Packaging and labeling	One glass pre-filled syringe packed in a patient kit box. Both the glass pre-filled syringe and the box will be labeled as required per country requirement.	One glass pre-filled syringe packed in a patient kit box. Both glass pre-filled the syringe and the box will be labeled as required per country requirement

^a Subcutaneous injection sites should alternate between the upper thighs, 4 quadrants of the abdomen or the upper arms, so that the same site is not injected twice during consecutive administrations. Injection in the upper arms can only be done by a trained person (parent/legally authorized representative/caregiver trained by Investigator or Delegate) or health care professional but not the participant themselves.

IMP: investigational medicinal product; NIMP: noninvestigational medicinal product.

The Investigator or delegate will train the patient (or caregiver) how to prepare and inject IMP at Visit 2. He/she will inject the first of the two injections. The participant (or caregiver) will perform the second injection under the supervision of the Investigator or delegate. Patient should also be trained by the site staff to recognize potential signs and symptoms of hypersensitivity reaction in order to self-monitor at home for at least 30 minutes (or longer per country specific or local site-specific requirements) following injection. In case of hypersensitivity symptoms the patient should contact healthcare provider/emergency. The training must be documented in the participant's study file.

When the participant has a study visit, the IMP will be administered following clinical procedures and blood collection. Patients should be monitored for at least 30 minutes. The monitoring period may be extended as per country specific or local site-specific requirements.

Between the protocol-scheduled on-site visits, participants are allowed to self-inject IMP at home. Participants who prefer to have a healthcare professional administer the IMP may choose to have injections administered at home by a nurse or at the study site.

Between the protocol-scheduled on-site visits, interim visits may be required for IMP dispensing. As an alternative to these visits, dupilumab 300 mg or matching placebo may be supplied from the site to the participant via a Sponsor-approved courier company where allowed by local regulations and approved by the participant.

6.1.1 Noninvestigational medicinal products

Starting from the screening visit, participants will be instructed to use their daily moisturizer, if it is not containing any compound with known anti-itch effect (such as menthol, polidocanol, pramoxine, lidocaine, prilocaine, capsaicin, naltrexone, N-palmitoylethanolamine, etc). It is not authorized changing emollients or moisturizers or applying products for itching relief during the course of the study.

Participants will be required to apply moisturizers (emollients) once or twice daily for at least 5 out of the 7 consecutive days immediately before Day 1 and continue until Week 36. All types of moisturizers are permitted, but patients may not initiate new treatment with prescription moisturizers or over-the-counter moisturizers containing additives during the screening period or during the intervention period. Patients may continue using stable doses of such moisturizers if initiated before the screening visit.

If participants are on a stable regimen of low to medium potency TCS or TCI at the screening visit, they can continue their topical steroid application once daily without tapering from Screening to Week 24. If specific lesions resolve, the participant can stop applying steroids to those sites but are permitted to continue applying to persistent lesions. If participants are on stable regimens of high potency or superpotent steroids, participants should decrease potency to medium potency TCS and continue to apply daily from screening to Week 24. Stable regimen for TCS is maintaining the same medicine (low to medium potency TCS), and maintaining the same frequency of treatment (once or twice daily) used from 2 weeks prior to screening. Stable regimen for TCI is maintaining the same medicine of TCI and the treatment frequency (once or twice daily) used from 2 weeks prior to screening. If participant's prior regimen was applying once daily, the participant will maintain daily application during study and for participants who had twice daily prior to screening, participation will maintain twice daily regimen during study. If specific lesions resolve, the participant can stop applying steroids to those sites but are permitted to continue applying to persistent lesions. Occlusion is not allowed from Screening to Week 24.

It is recommended that patients use triamcinolone acetonide 0.1% cream or fluocinolone acetonide 0.025% ointment for medium potency, and hydrocortisone 1% cream for low potency. If rescue with TCS is needed, it is recommended that patients use either betamethasone dipropionate 0.05% optimized ointment for high potency TCS or clobetasol propionate 0.05% cream for super high potency TCS. If patients have tolerance issues with any of these steroids or if they are not commercially available in some countries, they may substitute with products of the same potency from the list provided by the Sponsor.

On areas treated with TCS, moisturizers must be applied once daily only at the time when TCS is not applied (ie, do not use moisturizers and TCS on the same areas at the same time during the day). For example, if TCS are applied in the evening, moisturizers will not be used in the evening on areas treated with TCS, but will be applied to those areas in the morning. On areas not treated with TCS, moisturizers will be applied twice daily - morning and evening.

Rescue therapy is described in [Section 6.5.1](#).

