- E 17. Exposure to another systemic or topical investigative drug (monoclonal antibodies as well as small molecules) within a certain time period prior to Visit 1 (screening), as follows: an interval of less than 6 months or <5 PK half-lives for investigative monoclonal antibodies, whichever is longer, and an interval of less than 30 days or <5 PK half-lives, whichever is longer, for investigative small molecules.
- E 18. Having used any of the following treatments within 4 weeks before the screening visit
 - Systemic immunosuppressive/immunomodulating drugs (eg, systemic corticosteroids, cyclosporine, mycophenolate-mofetil, interferon gamma, Janus kinase inhibitors, azathioprine, methotrexate, hydroxychloroquine, dapsone, sulfasalazine, colchicine, etc),
 - Intralesional corticosteroid injections and cryotherapy,
 - Phototherapy, including tanning beds,

- Naltrexone or other opioid antagonist,
- Gabapentin, pregabalin, and thalidomide.

Or starting to use the following treatments or changed the dose of the following treatments in 3 months before the screening visit or expected the dose of the following treatments will be changed throughout the study:

- Paroxetine, fluvoxamine, or other selective serotonin reuptake inhibitors (SSRIs),
- Serotonin and norepinephrine reuptake inhibitors (SNRIs),
- Amitriptyline or other tricyclic or tetracyclic antidepressants.

E 19. Previous treatment with biologic medicines within the following timeframe:

- Any cell-depleting agents including but not limited to rituximab: within 6 months before the screening visit,
- Omalizumab: within 5 months before screening visit,
- Other immunomodulatory biologics: within 5 half-lives (if known) or 16 weeks before the screening visit, whichever is longer.

E 20. Initiation of treatment with prescription moisturizers or moisturizers containing additives such as ceramide, hyaluronic acid, urea, menthol, polidocanol, or filaggrin degradation products during the screening period (patients may continue using stable doses of such moisturizers if initiated before the Screening visit).

E 21. Initiation of treatment with TCS/TCI (any potency) during the screening period or treatment with high potency or superpotent TCS/TCI during the screening period.

E 22. For participants who were on a stable regimen of TCS/TCI (maintain same medicine, same dose from 2 weeks prior to screening visit) at the screening visit:

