6.5 CONCOMITANT THERAPY

Any medication or vaccine (including over-the-counter or prescription medicines, vitamins, and/or herbal supplements) that the participant is receiving at the time of enrollment or receives during the study must be recorded along with:

- Reason for use.
- Dates of administration including start and end dates.
- Dosage information including dose and frequency.

The concomitant use of non-sedating antihistamine administration is allowed during the study except for treatment of AD or PN, but dose change of non-sedating antihistamine is not allowed both from Week 11 to Week 12 and from Week 23 to Week 24.

The concomitant use of the following therapies is prohibited during the entire study. Study treatment will need to be discontinued in participants receiving these treatments:

- Systemic immunosuppressive/immunomodulating drugs (eg, systemic corticosteroids, cyclosporine, mycophenolate-mofetil, interferon gamma, Janus kinase inhibitors, azathioprine, methotrexate, hydroxychloroquine, dapsone, sulfasalazine, colchicine, etc).
- Other monoclonal antibodies (which are biological modifiers).
- Phototherapy, including tanning beds.
- Naltrexone or other opioid antagonist.
- Gabapentin, pregabalin, and thalidomide.

The concomitant use of the following therapies is prohibited except if the dose has been stable for at least 3 months prior to screening, but study treatment will not need to be discontinued in participants receiving the treatments listed below. The dose should also remain stable (can be reduced or discontinued if medically indicated), but should not be initiated or increased throughout the study.

- Paroxetine, fluvoxamine, or other SSRIs.
- SNRIs.
- Amitriptyline or other tricyclic or tetracyclic antidepressants.

The concomitant use of the following therapies is also prohibited during the entire study, but study treatment will not need to be discontinued in participants receiving the treatments listed below.

- Intralesional corticosteroid injections and cryotherapy.
- Sedating antihistamine.
- Non-sedating antihistamine used specifically for the treatment of itch secondary to AD or PN.

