4.3 PRIMARY ENDPOINT(S) ANALYSIS

4.3.1 Definition of endpoint(s)

The primary endpoint for this study is the proportion of participants with improvement (reduction) in worst-itch numeric rating scale (WI-NRS) by ≥ 4 from baseline to Week 24.

WI-NRS is a patient-reported outcome (PRO) comprised of a single item rated on a scale from 0 (“No itch”) to 10 (“Worst imaginable itch”). Participants are asked to rate the intensity of their worst pruritus (itch) over the past 24 hours using this scale.

The weekly average WI-NRS score at each week, which is defined as the average of daily non-missing scores within the week window of each week (see [Section 5.4](#)), will be used for analyses.

For efficacy analysis, [Table 5](#) presents the prohibited and rescue medications/procedures which will be considered as intercurrent events if the last column indicates as “Yes” and therefore be handled in the estimands for endpoints defined in [Table 3](#).

Table 5 - Prohibited medications/procedures and rescue medications that impact efficacy

Medication/procedure	Comment	Data to be set as non-responder after taking medication in the main statistical analysis (Yes/No) ^a /Selection criteria
Prohibited medications/procedures		
Systemic immunosuppressive/immunomodulating drugs (eg, systemic corticosteroids, cyclosporine, mycophenolate-mofetil, interferon gamma, Janus kinase inhibitors, azathioprine, methotrexate, hydroxychloroquine, dapsone, sulfasalazine, colchicine, etc)	IMP to be discontinued	Yes (CDG ^b Immunosuppressant drugs Narrow and SDG ^b Corticosteroids Narrow)
Other monoclonal antibodies (that are biological response modifiers).	IMP to be discontinued	Yes (SDG ^b SDGMonoclonal antibodies Narrow)
Phototherapy, including tanning beds.	IMP to be discontinued	Yes (CMQ ^b HLT Phototherapies, CMQ ^b Tanning_single PT)
Naltrexone or other opioid antagonist	IMP to be discontinued	Yes (SDG ^b Analgesia producing opioids NARROW)
Gabapentin, pregabalin, and thalidomide	IMP to be discontinued	Yes (CDG ^b Gabapentin mono and multi ingredients, Pregabalin mono and multi ingredients, or Thalidomide mono and multi ingredients)
Paroxetine, fluvoxamine or other SSRIs.	No IMP discontinuation, see requirement in the footnote	Yes ^{c,d} (CDG ^b N06AB selective serotonin reuptake inhibitors)
SNRIs.	No IMP discontinuation, see requirement in the footnote	Yes ^{c,d} (CDG ^b serotonin and norepinephrine reuptake inhibitors)

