5.7 APPENDIX 7 MEDICATION/PROCEDURE ADJUDICATION ALGORITHM

Algorithm for determining whether treatment with following medications or procedures constitutes treatment failure resulting in setting data as non-responder after taking medication or undergoing procedure in the main statistical analysis

1. Not required to adjudicate post-baseline medications (WHODD-coded) or procedures (CMQ-coded) as these will be considered treatment failures if used at any time¹.
 - a) Always considered treatment failure
 - ATC2 = CORTICOSTEROIDS FOR SYSTEMIC USE
 - ATC2=IMMUNOSUPPRESSANTS (systemic, eg, oral or parenteral route)
 - Preferred Drug Name = Ciclosporin
 - Preferred Drug Name = Methotrexate
 - Preferred Drug Name = Mycophenolate sodium
 - Preferred Drug Name = Mycophenolic acid
 - Preferred Drug Name = Azathioprine
 - Preferred Drug Name = Gabapentin
 - Preferred Drug Name = Pregabalin
 - Preferred Drug Name = Thalidomide
 - Preferred Drug Name = Lenalidomide
 - Preferred Drug Name = Baricitinib
 - Preferred Drug Name = Ruxolitinib
 - Preferred Drug Name = Tofacitinib
 - Preferred Drug Name = AbrocitinibPreferred Drug Name = Delgocitinib
 - Preferred Drug Name = Nalbuphine
 - Preferred Drug Name = Naltrexone
 - Preferred Drug Name = Naloxone
 - Preferred Drug Name = Vixarelimab
 - Preferred Drug Name = Nemolizumab
 - Preferred Drug Name = Serlopitant
 - Preferred Drug Name = Aprepitant
 - CMQb HLT Phototherapies
 - CMQ Tanning_single PT
 - b) Never considered treatment failure:
 - ATC2 = EMOLLIENTS AND PROTECTIVES

- ATC2 = GENERAL NUTRIENTS
- ATC2 = VITAMINS
- ATC2 = ANTIVIRALS FOR SYSTEMIC USE
- ATC2 = ANTIFUNGALS FOR DERMATOLOGICAL USE
- ATC2 = ANTISEPTICS AND DISINFECTANTS
- ATC2 = ANTIBIOTICS AND CHEMOTHERAPEUTICS FOR DERMATOLOGICAL USE
- ATC2 = ANTI-ACNE PREPARATIONS, excluding D10AA Corticosteroids, combinations for treatment of acne
- ATC2 = OPHTHALMOLOGICALS
- ATC1 = ANTIINFECTIVES FOR SYSTEMIC USE, excluding D07C Corticosteroids, combinations with antibiotics
- ATC1 = BLOOD AND BLOOD FORMING ORGANS
- ATC1 = ALIMENTARY TRACT AND METABOLISM
- ATC1 = MUSCULO-SKELETAL SYSTEM, excluding M01BA Antiinflammatory/antirheumatic agents in combination with corticosteroids
- ATC2 = COUGH AND COLD PREPARATIONS
- ATC2 = PSYCHOLEPTICS, excluding N05BB Diphenylmethane derivatives and N05C HYPNOTICS AND SEDATIVES

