¹ A blinded review of all post-baseline medications or procedures to adjudicate whether treatment constitutes treatment failure, based on medical judgment, may be performed in addition. A listing of treatments or procedures classified as treatment failure in a manner inconsistent with the classification under #1 will be provided, along with supporting rationale.

2. Require to adjudicate medications or procedures that may constitute treatment failure

- All other medications and procedures listed in the protocol and [Table 5](#) of the SAP (not noted in 1. above) given for indications consistent with PN²
- Considerations in determining treatment failure include the criteria already set forth in [Table 5](#) of the SAP in addition to the type of medication or procedure, indication, dose, route of administration, timing, frequency and the potential impact of the use of the prohibited medications/procedures and rescue medications on the primary and key secondary efficacy endpoints.

2 Below is a list of indications consistent with PN based on PT level from concomitant medication/procedure data using MedDRA dictionary

System Organ Class	High Level Term	Preferred Term	Preferred Term Code
Skin and subcutaneous tissue disorders	Dermatitis and eczema	Neurodermatitis	10029263
Infections and infestations	Bacterial infections NEC	Eczema impetiginous	10051890
Infections and infestations	Skin structures and soft tissue infections	Dermatitis infected	10012470
Infections and infestations	Skin structures and soft tissue infections	Eczema infected	10014199
Skin and subcutaneous tissue disorders	Dermatitis and eczema	Dermatitis	10012431
Skin and subcutaneous tissue disorders	Dermatitis and eczema	Dermatitis atopic	10012438
Skin and subcutaneous tissue disorders	Dermatitis and eczema	Eczema	10014184

Signature Page for VV-CLIN-0602722 v5.0
efc16459-16-1-9-sap

Approve & eSign

Approve & eSign

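### Itch-relief products barred by Protocol 6.1.1 are not intercurrent events in SAP Table 5, so by default a response after starting one can count on the primary itch endpoint

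*Protocol*

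**What the plan says.** Protocol 6.1.1 lets participants use their daily moisturizer "if it is not containing any compound with known anti-itch effect (such as menthol, polidocanol, pramoxine, lidocaine, prilocaine, capsaicin, naltrexone" and one further compound, eight in all. It continues: "It is not authorized changing emollients or moisturizers or applying products for itching relief during the course of the study". Its second paragraph bars starting prescription moisturizers, or over-the-counter ones with additives, during screening or treatment, and then adds: "Patients may continue using stable doses of such moisturizers if initiated before the screening visit".

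Protocol 6.5 holds the lists of prohibited therapies. The last list opens "The concomitant use of the following therapies is also prohibited during the entire study, but study treatment will not need to be discontinued" and covers intralesional corticosteroids, cryotherapy and antihistamines. None of the lists mentions topical itch-relief products or moisturizers.

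SAP 4.3.1 says that Table 5 "presents the prohibited and rescue medications/procedures which will be considered as intercurrent events if the last column indicates as" Yes. SAP 4.3.2 ties primary non-response to Table 5 use before Week 24 or to missing Week 24 data. Table 5 has no row for topical anti-itch products or moisturizers.

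SAP Appendix 7 item 1b, the list of treatments that never count as failure, includes "ATC2 = EMOLLIENTS AND PROTECTIVES" without exception. Footnote 1 allows a blinded review of all post-baseline treatments, which, "based on medical judgment, may be performed in addition", can depart from the lists with a rationale. In the SAP version history, the version 3.0 row that explains the removal of the word 'selected' says that taking any prohibited medication specified in the protocol leads to non-response after blinded adjudication.

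**The concern.** The primary endpoint is a 4-point fall in worst itch, and these products are barred because they act on itch. An antihistamine taken for itch is in Table 5; a topical product barred for the same reason is not. If a participant's itch falls because of a barred product, the primary analysis can credit that fall to the randomized arm.

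Participants whose study treatment is not working have the most reason to reach for such products. More use on placebo is therefore plausible, and it would raise placebo response and shrink the difference. The same rules govern the combined itch-and-lesion key secondary endpoint, percent change in WI-NRS and time to response.

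**Working it through.** **Tracing the rule.** The main question is one of text, so each place where use of a barred product could be caught is checked in turn.

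| Place | Does it catch a barred topical started on study? |
|---|---|
| Protocol 6.5 lists | No; not listed |
| SAP Table 5 | No row. Of the eight compounds named in 6.1.1, only naltrexone is covered |
| Appendix 7 item 1a (always failure) | Naltrexone only |
| Appendix 7 item 1b (never failure) | Exempts anything coded to the emollient class. Neighbouring entries carry exclusions (for example acne products with corticosteroids); this one does not |
| Appendix 7 item 2 (adjudicate) | Unclear. It covers other treatments named in the protocol and in Table 5, given for PN-consistent indications. The indication list in footnote 2, as shown, has no pruritus or prurigo term |
| Appendix 7 footnote 1 | Could catch it, but the review is optional |
| Protocol 6.5.1 and SAP 5.3 review | Mandatory, but its purpose is to adjudicate rescue, and the rescue medications named are high-potency or superpotent TCS and TCI |
| SAP 4.3.1 blinded review | Mandatory, but based on Table 5 and Appendix 7 |
| SAP 4.2 deviations | Summarized only; responder status does not change |
| SAP 4.3.4 supplementary analyses | The as-observed analysis counts these data. The hybrid and tipping-point analyses act on prohibited or rescue use and on missing data |

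No mandatory step clearly catches the product.

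**Size, by assumption only.** The plan's 56 per arm (90% power, two-sided Fisher exact test at 0.05) cannot be reproduced because both response rates are redacted. Instead, take placebo rates p0 and solve for the dupilumab rate p1 that gives exactly 90% exact Fisher power at 56 per arm:

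| p0 | p1 | Power at 75 per arm |
|---|---|---|
| 10% | 36.6% | 96.9% |
| 15% | 43.7% | 96.8% |
| 20% | 50.1% | 96.6% |
| 25% | 56.4% | 97.2% |
| 30% | 62.0% | 97.5% |

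Let u and v be the shares of placebo and dupilumab participants who use a barred product, and r the share of users who become extra responders. The counted rates are p0 + u·r and p1 + v·r, so the difference falls by (u − v)·r. With r = 0.5:

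| u, v | Fall in difference | Power at 75 per arm |
|---|---|---|
| 2%, 1% | (0.02 − 0.01) × 0.5 = 0.5 points | 96-97% |
| 5%, 5% | 0; both rates rise by 0.05 × 0.5 = 2.5 points | 96-97% |
| 10%, 3% | (0.10 − 0.03) × 0.5 = 3.5 points | 87-93% |
| 15%, 5% | (0.15 − 0.05) × 0.5 = 5 points | 80-90% |

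This takes every extra responder as one who would not have responded otherwise. If instead half of all users respond in total, the counted rate is p + u(0.5 − p). For 10% and 3% use with p0 = 10%, the fall is 0.10 × (0.5 − 0.10) − 0.03 × (0.5 − 0.366) = 3.6 points. With p0 = 30% it is 0.10 × (0.5 − 0.30) − 0.03 × (0.5 − 0.62) = 2.4 points. Power is then 88-95%.

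If use were higher on dupilumab, the sign would reverse: with 3% on placebo and 10% on dupilumab, the difference widens by 3.5 points under the first formula.

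**The case against.** Item 2 of Appendix 7 can be read as a union: treatments named in the protocol, together with those in Table 5. On that reading, pramoxine, lidocaine or capsaicin, which 6.1.1 names, would go to adjudication. The version 3.0 rationale supports this. The point stands against any claim that such products certainly escape. It does not close the gap: 4.3.1 and 4.3.2 rest on Table 5, emollients are already settled under item 1b, and item 2 still requires a PN-consistent indication.

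A reader might also infer that every anti-itch moisturizer is exempt. The documents do not show how products are coded, so this holds only for those coded to the emollient class. Some exemption is needed in any case, since all participants must use moisturizer until Week 36. A product coded elsewhere still has no Table 5 row.

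It is fair to say that a barred product need not be an intercurrent event. Table 5 footnote a applies treatment policy to items marked No. But these products are not marked No; they are absent, and the stated intent is non-response.

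The mandatory reviews do bring medical judgment to post-baseline medications before lock. Their stated scope, however, is rescue or prohibited treatment as Table 5 and Appendix 7 define it.

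Finally, the use rates are pure assumption, and dilution would not create a false positive. Both points are accepted.

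**Conclusion.** The gap is real. Protocol 6.1.1 bars these products, the lists that drive the analysis do not carry the ban, and by default a 4-point drop after starting one can count as response. This departs from the SAP's own stated intent.

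The documents do not support the stronger inference that power will fall to 80-90% or that the estimate will be biased in a known direction. They give no use rates, and the response rates are redacted. The power figures also take the assumed rates as those of all 75 randomized per arm. At low use the effect on power is negligible.

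The point covers products started on study only. For moisturizers used before screening, the first paragraph of 6.1.1 rules out anti-itch compounds, while its second paragraph allows stable use of additive-containing products to continue. Exclusion criterion E 20, which names menthol and polidocanol among the additives, says that "patients may continue using stable doses of such moisturizers if initiated before the Screening visit". The sponsor must reconcile these passages. No view is taken here on which should prevail.

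**What to change.** Before lock and while blinded:

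1. Add a row to SAP Table 5 for topical products for itch relief, or moisturizers containing an anti-itch compound named in Protocol 6.1.1, started after baseline. Mark it Yes, per blinded adjudication (footnote d).
2. In Appendix 7 item 1b, exclude from the emollient class only such products started after baseline, and send them to item 2. State there that use for itch, pruritus or PN qualifies for adjudication whether or not the term is on the footnote 2 list.
3. Cross-refer Protocol 6.5 to 6.1.1 so that the lists agree.

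Continued use of a moisturizer begun before screening is outside this change and waits on the reconciliation of 6.1.1 with E 20.

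The cost is wording. Protocol 6.5 already requires over-the-counter products to be recorded with reason and dates, so no new data are needed. A few more participants will be adjudicated, and some may become non-responders.
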